## **2. STUDY OBJECTIVES**

The objectives of Part A and Part B are provided below.

### **2.1 PRIMARY OBJECTIVE**

The primary objectives for Part A of the study are as follows:

- To examine the effect of food on the single dose PK of plixorafenib administered with cobicistat.
- To examine the effect of cobicistat administration on the single dose PK of plixorafenib.
- To determine the safety of plixorafenib administered alone and with cobicistat in a single dose regimen in healthy participants.

The primary objectives for Part B of the study are:

- To examine the effect of a high-fat and a low-fat meal versus fasted state on the single dose PK of plixorafenib administered alone.
- To examine the effect of a low-fat meal versus fasted state on the single dose PK of plixorafenib administered with cobicistat.
- To determine the safety of plixorafenib administered alone or with cobicistat (low-fat meal only) in a single dose regimen.

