**Table 3-1 Study Description for Part A**

Treatment Period	Screening	Check-in	Dosing	Confinement
1	Day -28 to -1	Day -1	Day 1	Day -1 to Day 19 (EOS)
2	N/A	N/A	Day 8	
3	N/A	N/A	Day 15	

N/A, not applicable; EOS, end of study

There will be a 7-day washout between dosing in each treatment period.

EOS visit will be conducted on Day 19.

A screening evaluation will be performed to determine each participant's eligibility for the study approximately 28 to 1 days before the first dose. Participants eligible for participation will report to the study facility 1 day before dosing in Treatment Period 1 for check-in.

On Day 1 of Treatment Period 1, eligible participants will be randomized to 1 of 6 treatment sequences: 1:2:3, 2:3:1, 3:2:1, 2:1:3, 3:1:2, 1:3:2. On the first day of each treatment period, each participant will receive one of the following treatments according to the sequence in which he or she is randomized:

- Treatment 1: 900 mg plixorafenib administered after overnight fast (fasted state).
- Treatment 2: 900 mg plixorafenib + 150 mg cobicistat administered after overnight fast (fasted state).
- Treatment 3: 900 mg plixorafenib + 150 mg cobicistat administered following a high fat, high caloric meal (fed state).

For Treatment 2 and Treatment 3, plixorafenib and cobicistat will be co-administered.

All participants will fast overnight (nothing to eat or drink except water) for at least 10 hours. Participants receiving Treatments 1 and 2 (fasted condition) will continue to fast for at least 4 hours after dosing.

Participants receiving Treatment 3 will receive a standard high fat ( $\geq 50\%$  of the total caloric content of the meal), high caloric meal (approximately 800 to 1000 calories) for breakfast before dosing and this meal should derive approximately 150, 250, and 500 to 600 calories from protein, carbohydrate, and fat, respectively (DHHS 2022). Participants must consume the entire meal within 30 minutes of serving; the percentage of meal consumed will be documented. Dosing must occur 30 minutes ( $\pm 5$  minutes) after the start of the meal. Participants receiving Treatment 3 will receive their next meal no less than 4 hours after dosing.

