**Table 3-2 Study Description for Part B**

Treatment Period	Screening	Check-in	Dosing	Confinement
1	Day -28 to -1	Day -1	Day 1	Day -1 to Day 19 (EOS)
2	N/A	N/A	Day 8	
3	N/A	N/A	Day 15	

N/A, not applicable; EOS, end of study.

There will be a 7-day washout between dosing in each treatment period. EOS visit will be conducted on Day 19.

A screening evaluation will be performed to determine each participant's eligibility for the study approximately 28 to 1 days before the first dose. Participants eligible for participation will report to the study facility 1 day before dosing in Treatment Period 1 for check-in.

On Day 1 of Treatment Period 1, eligible participants will be randomized to 1 of 4 treatment sequences: A:C:D, B:D:A, D:B:C, C:A:B. On the first day of each treatment period, each participant will receive one of the following treatments according to the sequence in which he or she is randomized:

- Treatment A: 900 mg plixorafenib administered after overnight fast (fasted state).
- Treatment B: 900 mg plixorafenib administered following a high-fat high caloric meal (fed state-high fat meal).
- Treatment C: 900 mg plixorafenib administered following a low-fat meal (fed state-low-fat meal).
- Treatment D: 900 mg plixorafenib administered with 150 mg cobicistat following a low-fat meal (fed state-low-fat meal).

All participants will fast overnight (nothing to eat or drink except water) for at least 10 hours.

- Participants receiving Treatment A (fasted condition) will continue to fast for at least 4 hours after dosing.
- Participants receiving Treatment B will receive a high fat ( $\geq 50\%$  of the total caloric content of the meal), high caloric meal (approximately 800 to 1000 calories) for breakfast before dosing and this meal should derive approximately 150, 250, and 500 to 600 calories from protein, carbohydrate, and fat, respectively.
- Participants receiving Treatments C and D will receive a low-fat meal (approximately 400 to 500 total calories, with 25% of the total caloric content of the meal from fat) for breakfast before dosing.

All participants receiving Treatments B, C, or D must consume the entire meal within 30 minutes of serving; the percentage of meal consumed will be documented. Dosing must occur 30 minutes ( $\pm 5$  minutes) after the start of the meal. Participants receiving Treatments B, C, and D will receive their next meal no less than 4 hours after dosing.

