### 5.2 STUDY DRUGS

The study drugs that will be used are as follows:

Product	Supplied Formulation
Plixorafenib	150 mg tablet
Cobicistat	150 mg tablet

Plixorafenib is available as white to off-white oval tablet (uncoated or film-coated tablets) and contains the following inactive excipients: HPMCAS, sodium lauryl sulfate, microcrystalline cellulose, mannitol, croscarmellose sodium, silicon dioxide, and sodium stearyl fumarate. Film-coated tablets also contain titanium dioxide, polyvinyl alcohol, macrogol, and talc.

Further information on the study drug can be found in the Investigator's Brochure (Fore Biotherapeutics 2023).

Cobicistat (150 mg) tablet is commercially available and will be supplied or obtained by the clinical unit according to the study agreement and in accordance with local guidelines. Refer to the prescribing of cobicistat for more details on the formulation, preparation, storage conditions, the approved indications, known precautions, warnings, and adverse reactions. Cobicistat will be dispensed by the pharmacy staff at the clinical study site.

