 - 900 mg plixorafenib + 150 mg cobicistat (Low Fat)

In addition to analysis by Part A and Part B, pooled analysis by treatment may be conducted as exploratory analysis.

All data listings will be sorted by participant number and collection date where applicable.

No algorithm for imputation of missing data will be employed.

For Part A and B, study days are calculated with respect to the first dose date of any study drug as below:

- If the assessment/observation date is on or after the first dose date of any study drug, then
Study Day = Assessment/Observation Date – First Dose Date of any study drug + 1;
- Otherwise,
Study Day = Assessment/Observation Date – First Dose Date of any study drug.

Unless stated otherwise, for safety analysis in Part A and B, baseline will be defined as the last non-missing assessment (including repeat and unscheduled assessments) pre-dose for each period. This may include a post-dose assessment for the previous period (for example, Day 4 assessment of Treatment Period 1 may be considered a baseline assessment for Treatment Period

2 when a subject has no pre-dose assessments for period 2). Unless stated otherwise, baseline for analysis by sequence is defined as the last assessed value prior to dosing on Day 1 of Period 1.

For summaries of safety assessments, if there are repeated measurements at a time point, the first non-missing assessment at that time point will be used in the summary tables.

For summaries of safety assessments, the maximum and minimum postbaseline result (where applicable), will be selected as the highest and lowest result (respectively) collected after baseline, including repeated and unscheduled assessments.

Unscheduled results will not be included in the summary tables by visit, except for determining Baseline or postbaseline minimum and maximum, but will be presented in data listings.

For Part A and B, to compare the post baseline results of the same treatment across different treatment periods, summaries by treatment and timepoint will standardize the visits as follows:

Analysis Visit	Recorded Visit
Baseline	Baseline result as defined above
Day 2	Day 2, Day 9, or Day 16
Day 3	Day 3, Day 10, or Day 17
Day 4	Day 4, Day 11, or Day 18
Day 5	Day 5, Day 12, or Day 19/EOS

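### Part B's second primary objective (low-fat meal versus fasted, both with cobicistat) cannot be answered within Part B; it needs a cross-part contrast that the protocol and SAP do not prespecify

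*Protocol*

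**What the plan says.** Protocol section 2.1, repeated in the synopsis and in SAP section 2.1, lists as a primary objective of Part B: "To examine the effect of a low-fat meal versus fasted state on the single dose PK of plixorafenib administered with cobicistat".

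Protocol section 3.2 says that "eligible participants will be randomized to 1 of 4 treatment sequences: A:C:D, B:D:A, D:B:C, C:A:B". SAP Table 3-4 gives the same sequences. All treatments use 900 mg plixorafenib, and cobicistat is 150 mg where given:

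| Part | Treatment | Cobicistat | Food state |
|---|---|---|---|
| A | 1 | no | fasted |
| A | 2 | yes | fasted |
| A | 3 | yes | high-fat meal |
| B | A | no | fasted |
| B | B | no | high-fat meal |
| B | C | no | low-fat meal |
| B | D | yes | low-fat meal |

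Protocol section 7.3.1 describes a mixed model, to be run if warranted, with plixorafenib alone as the reference and plixorafenib with cobicistat and/or food as the tests. Where that section names treatments for the concentration summaries, it names only the three from Part A. It defers further detail to the SAP. SAP section 1 excludes the PK analysis and refers to a separate PK analysis plan; section 4 repeats this. The SAP's only cross-part provision is in section 4: "pooled analysis by treatment may be conducted as exploratory analysis".

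**The concern.** The objective needs two conditions that differ only in food: cobicistat with a low-fat meal, and cobicistat fasted. Part B has the first and not the second, so a primary objective has no matching comparison in the part of the study to which it is assigned.

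The question is central to the study. The recommended Phase 2 dose includes cobicistat (Protocol section 1.3). Part B was motivated by Part A's roughly 3-fold higher AUC and 2-fold higher Cmax when plixorafenib plus cobicistat was taken with a high-fat meal (Protocol section 1.2). Whether a lighter meal has a similar effect in the presence of cobicistat is what this objective asks.

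Following the model as described gives D a reference of plixorafenib alone. That ratio changes two factors at once, and the interaction rule in section 7.3.1 would be applied to a number that cannot separate them.

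**Working it through.** The documents give no power calculation and no within-participant CV, so there is no plan figure to reproduce. The check has three steps: whether the contrast is estimable, what the available contrasts measure, and how precise the cross-part route would be.

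**Inputs.** Part A: 12 participants, six sequences, 2 per sequence. Part B: 16 participants, four sequences, 4 per sequence. Two-sided 90% CI on the log scale; limits 80–125% (Protocol section 7.3.1). The within-participant CV is my assumption, ranged below. Write s² = ln(1 + CV²) for the within-participant log-scale variance.

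**1. Estimability.** From the four sequences, each treatment goes to 12 of the 16 Part B participants and each pair of treatments is shared by 8. With treatment, period and participant effects:

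- D versus cobicistat-fasted: not estimable from Part B at any sample size, because no Part B observation has cobicistat in the fasted state.
- C versus A, B versus A, D versus A, D versus C: all estimable.

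**2. What the available contrasts measure.** On the ratio scale, D/A = (cobicistat effect when fasted) × (low-fat meal effect with cobicistat). The second factor is the objective; the first is not observed in Part B. The documents put the cobicistat effect on exposure at about 2- to 3-fold (PLX120-03) and on AUC at 3.8-fold at 900 mg (PLX120-04, earlier formulation). If those figures applied here, D/A would be about 2 to 3.8 even if the low-fat meal did nothing. D/C is the cobicistat effect after a low-fat meal.

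**3. Precision of the cross-part route.** Treatment 1 in Part A and Treatment A in Part B have the same description, so the parts can be linked:

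log(D/Treatment 2) = [log D − log A] in Part B − [log Treatment 2 − log Treatment 1] in Part A

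- Part B term, balanced incomplete block with k = 3 periods, t = 4 treatments, λ = 8: 2ks²/(λt) = 6s²/32 = 0.1875 s².
- Part A term, complete crossover with n = 12: 2s²/12 = 0.1667 s².
- Sum: 0.354 s², so SE = 0.595 s. This is 0.354/0.1875 = 1.89 times the variance of a contrast inside Part B.

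Residual degrees of freedom with participant effects fixed are 84 − 37 = 47 for the two parts together and 48 − 21 = 27 for Part B alone. The 90% CI factor is exp(t × SE), with t = 1.678 and 1.703 respectively:

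| Assumed CV | s | Cross-part D vs Treatment 2 | Inside Part B, e.g. C vs A |
|---|---|---|---|
| 30% | 0.294 | ×/÷ 1.34 | ×/÷ 1.24 |
| 40% | 0.385 | ×/÷ 1.47 | ×/÷ 1.33 |
| 50% | 0.472 | ×/÷ 1.60 | ×/÷ 1.42 |
| 70% | 0.631 | ×/÷ 1.88 | ×/÷ 1.59 |

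With participant random and a fixed part effect, the variance is 0.345 to 0.352 s² for between/within variance ratios of 0.5 to 4, so the figures hardly move. Dropping the part effect lowers it to 0.258 to 0.316 s², but only by treating the two cohorts as exchangeable.

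The expected half-width reaches ln 1.25 = 0.223 when s = 0.223/(0.595 × 1.678) = 0.2235, a CV of about 23%. Simulating the interval with a true ratio of 1, it falls wholly inside 80–125% in about 5% of trials at CV 23%, 1.5% at 25% and 0.04% at 30%.

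**The case against.** The strongest reply is that the study as a whole can address the question. Part A Treatment 2 is the missing condition, the two parts share an anchor, Part B was designed after Part A was reviewed, and the SAP foresees pooling. This stands against a reading that the objective is unanswerable altogether. It does not rescue the plan as written: neither the protocol nor the SAP names Treatment 2 as the comparator, and the only pooling provision is optional and exploratory while the objective is primary.

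Second, the PK analysis plan was not available and may define the contrast. That is a real limit on what can be said about missing specification. It does not alter the objective as worded, nor the reference stated in Protocol section 7.3.1.

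Three stronger readings are tempting, and the documents do not support them:

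- A reader might infer that the sponsor intends D versus A as the meal effect. The protocol speaks of cobicistat and/or food and nowhere presents that ratio as a food effect.
- A reader might infer that most of D/A would be the cobicistat effect. The low-fat meal effect is unknown, and the roughly 3-fold AUC increase with the high-fat meal in Part A is of the same order as the cobicistat figures. The shares cannot be stated.
- A reader might infer that the cross-part interval could never fall inside 80–125% above a CV of about 23%. The realized width varies, so very unlikely is the right description.

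Finally, Protocol section 5.2 allows uncoated or film-coated tablets without tying either to a part. That is something to confirm, not evidence of a difference.

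**Conclusion.** The objective and the Part B treatment list do not match and must be reconciled. Within Part B, the low-fat versus fasted comparison with cobicistat is not estimable, and following the stated reference gives a ratio that confounds meal and cobicistat. This follows from the treatment list alone and rests on no assumption.

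An indirect cross-part estimate is available, with 1.89 times the variance of a contrast inside Part B and a 90% CI factor of about 1.34 to 1.47 at assumed CVs of 30% to 40%. It could show a 2-fold meal effect, but could rarely support a no-effect conclusion. It is not randomized across parts, and it assumes that the Treatment 2 versus Treatment 1 ratio seen in Part A would also hold in the Part B cohort. The precision figures assume that all 28 planned participants complete.

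**What to change.** In Protocol sections 2.1 and 7.3.1 and SAP section 2.1 (and in the PK analysis plan, if it does not already do so):

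- State that this objective is addressed by one prespecified cross-part contrast, Part B Treatment D versus Part A Treatment 2, anchored on plixorafenib alone fasted (Treatment 1 coded as the same treatment as A).
- Specify the model: log AUC and log Cmax, with treatment, part and period within part as fixed effects and participant as random. Keep the part effect, so that the comparison stays anchored.
- Report the ratio with its 90% CI, labelled non-randomized across parts and supportive, with no 80–125% verdict.
- State that D versus A is not a food-effect estimate, and report D versus C as the cobicistat effect after a low-fat meal.
- Confirm and record whether the tablet presentation was the same in both parts.

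The cost is rewording and one additional model on data that the study already plans to collect; no extra participants are needed. The downside is a weaker claim: a primary objective would rest on a supportive cross-part estimate.

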## **2.2 SECONDARY OBJECTIVES**

The secondary objectives for Part A of the study are as follows:

- To characterize metabolites of plixorafenib in plasma and urine.
- To characterize the urinary excretion of plixorafenib.

There are no secondary objectives for Part B of the study.

## **2.3 EXPLORATORY OBJECTIVE**

The exploratory objective for Part A and Part B of the study is as follows:

- To examine the possible effect of pharmacogenomic variations on the PK of plixorafenib and/or the effect of cobicistat, including polymorphisms in P-gp, BCRP, and UGT.

The exploratory objective for Part B of the study is as follows:

- The effect of single dose administration of plixorifenib on endogenous biomarkers such as coproporphyrin may be evaluated.

## **3. STUDY DESIGN**

This is a Phase 1, open-label, 2-part, single dose, crossover, single-center study.

### **3.1 PART A**

Part A is an open-label, randomized, single dose, 3-treatment, 3-period, crossover study designed to assess the effect of food and cobicistat administration on the PK and safety of plixorafenib in 12 healthy adult participants.

The study will consist of a screening period, 1 check-in, 3 treatment periods (with a 7-day washout between dosing in each period), and an EOS visit as illustrated in Table 3-1:

**Table 3-1 Study Description for Part A**

Treatment Period	Screening	Check-in	Dosing	Confinement
1	Day -28 to -1	Day -1	Day 1	Day -1 to Day 19 (EOS)
2	N/A	N/A	Day 8	
3	N/A	N/A	Day 15	

N/A, not applicable; EOS, end of study

There will be a 7-day washout between dosing in each treatment period.

EOS visit will be conducted on Day 19.

A screening evaluation will be performed to determine each participant's eligibility for the study approximately 28 to 1 days before the first dose. Participants eligible for participation will report to the study facility 1 day before dosing in Treatment Period 1 for check-in.

On Day 1 of Treatment Period 1, eligible participants will be randomized to 1 of 6 treatment sequences: 1:2:3, 2:3:1, 3:2:1, 2:1:3, 3:1:2, 1:3:2. On the first day of each treatment period, each participant will receive one of the following treatments according to the sequence in which he or she is randomized:

- Treatment 1: 900 mg plixorafenib administered after overnight fast (fasted state).
- Treatment 2: 900 mg plixorafenib + 150 mg cobicistat administered after overnight fast (fasted state).
- Treatment 3: 900 mg plixorafenib + 150 mg cobicistat administered following a high fat, high caloric meal (fed state).

For Treatment 2 and Treatment 3, plixorafenib and cobicistat will be co-administered.

All participants will fast overnight (nothing to eat or drink except water) for at least 10 hours. Participants receiving Treatments 1 and 2 (fasted condition) will continue to fast for at least 4 hours after dosing.

Participants receiving Treatment 3 will receive a standard high fat ( $\geq 50\%$  of the total caloric content of the meal), high caloric meal (approximately 800 to 1000 calories) for breakfast before dosing and this meal should derive approximately 150, 250, and 500 to 600 calories from protein, carbohydrate, and fat, respectively (DHHS 2022). Participants must consume the entire meal within 30 minutes of serving; the percentage of meal consumed will be documented. Dosing must occur 30 minutes ( $\pm 5$  minutes) after the start of the meal. Participants receiving Treatment 3 will receive their next meal no less than 4 hours after dosing.

All study drugs will be administered orally with approximately 240 mL of room temperature water. Water (except water provided with each dosing) will be restricted 1 hour prior to and 1 hour after each study drug administration, except for any fluid (ie, water, milk, juice) provided with the predose meal (Treatment 3 only), but will be allowed ad libitum at all other times. Up to an additional 240 mL of water will be allowed, if necessary, to aid in swallowing the study drugs when both study drugs are administered simultaneously.

Participants will remain at the facility from check-in (Day -1) to EOS and would be able to leave the facility upon satisfactory safety review. During confinement, participants will receive standardized meals per the clinic's standard procedures that are scheduled at the same time in each period of the study. Participants will be discharged from the study on Day 19 (Treatment Period 3).

The duration of the study for each participant, excluding screening period, will be approximately 20 days. Including screening period, the total study duration for each participant will be 48 days.

## 3.2 PART B

Part B is an open-label, randomized, single dose, 4-treatment, 3-period, crossover study designed to assess the effect of food (either a high-fat meal or a low-fat meal) on the PK and safety of plixorafenib administered alone or with cobicistat (low-fat meal only) in 16 healthy adult participants.

This part will consist of a screening period, 1 check-in, 3 treatment periods (with a 7-day washout between dosing in each period), and an EOS visit as illustrated in Table 3-2:

**Table 3-2 Study Description for Part B**

Treatment Period	Screening	Check-in	Dosing	Confinement
1	Day -28 to -1	Day -1	Day 1	Day -1 to Day 19 (EOS)
2	N/A	N/A	Day 8	
3	N/A	N/A	Day 15	

N/A, not applicable; EOS, end of study.

There will be a 7-day washout between dosing in each treatment period. EOS visit will be conducted on Day 19.

A screening evaluation will be performed to determine each participant's eligibility for the study approximately 28 to 1 days before the first dose. Participants eligible for participation will report to the study facility 1 day before dosing in Treatment Period 1 for check-in.

On Day 1 of Treatment Period 1, eligible participants will be randomized to 1 of 4 treatment sequences: A:C:D, B:D:A, D:B:C, C:A:B. On the first day of each treatment period, each participant will receive one of the following treatments according to the sequence in which he or she is randomized:

- Treatment A: 900 mg plixorafenib administered after overnight fast (fasted state).
- Treatment B: 900 mg plixorafenib administered following a high-fat high caloric meal (fed state-high fat meal).
- Treatment C: 900 mg plixorafenib administered following a low-fat meal (fed state-low-fat meal).
- Treatment D: 900 mg plixorafenib administered with 150 mg cobicistat following a low-fat meal (fed state-low-fat meal).

All participants will fast overnight (nothing to eat or drink except water) for at least 10 hours.

- Participants receiving Treatment A (fasted condition) will continue to fast for at least 4 hours after dosing.
- Participants receiving Treatment B will receive a high fat ( $\geq 50\%$  of the total caloric content of the meal), high caloric meal (approximately 800 to 1000 calories) for breakfast before dosing and this meal should derive approximately 150, 250, and 500 to 600 calories from protein, carbohydrate, and fat, respectively.
- Participants receiving Treatments C and D will receive a low-fat meal (approximately 400 to 500 total calories, with 25% of the total caloric content of the meal from fat) for breakfast before dosing.

All participants receiving Treatments B, C, or D must consume the entire meal within 30 minutes of serving; the percentage of meal consumed will be documented. Dosing must occur 30 minutes ( $\pm 5$  minutes) after the start of the meal. Participants receiving Treatments B, C, and D will receive their next meal no less than 4 hours after dosing.

Plixorafenib will be administered orally with approximately 240 mL of room temperature water. Water (except water provided with each dosing) will be restricted 1 hour before and 1 hour after each study drug administration, except for consuming any fluid (eg, water, milk, juice) provided with the predose meal (Treatments B, C, and D) but will not be limited at other times. Up to an additional 240 mL of water will be allowed, if necessary, to aid in swallowing the study drugs when administered with cobicistat (Treatment D).

Participants will remain at the facility from check-in (Day -1) to EOS and would be able to leave the facility upon satisfactory safety review by the investigator. During confinement periods, participants will receive standardized meals per the clinic's standard procedures that are scheduled at the same time in each period of the study. Participants will be discharged from the study on Day 19 (Treatment Period 3).

The duration of the study for each participant, excluding screening, will be approximately 20 days. Including screening, the total study duration for each participant will be 48 days.

